5.3.3 Clinical/Laboratory criteria

14. History of seizure, including any febrile seizure, loss of consciousness, or transient ischemia attack within 12 months of enrollment (Day 1 visit), or any

condition that may pre-dispose to seizure (e.g., prior stroke, brain arteriovenous malformation, head trauma with loss of consciousness requiring hospitalization)

15. Clinically significant cardiovascular disease including:

- Myocardial infarction within 6 months
- Uncontrolled angina within 3 months
- Congestive heart failure New York Heart Association (NYHA) class 3 or 4, or patients with history of congestive heart failure NYHA class 3 or 4 in the past, unless a screening echocardiogram or multi-gated acquisition scan (MUGA) performed within 3 months results in a left ventricular ejection fraction that is \geq 45%
- Hypotension (systolic blood pressure $<$ 86 millimeters of mercury [mmHg] or bradycardia with a heart rate $<$ 50 beats per minute;
- Uncontrolled hypertension as indicated by a resting systolic blood pressure of 170 mmHg or diastolic blood pressure $>$ 105 mmHg at the Screening or Study Day 1 visit;

16. Gastrointestinal disorder affecting absorption (e.g., gastrectomy, active peptic ulcer within last 3 months)

17. Major surgery within 4 weeks prior to enrollment (Day 1 visit)

18. Absolute neutrophil count $<$ 1,500/ μ L, platelet count $<$ 100,000/ μ L, and hemoglobin $<$ 5.6 mmol/L (9 g/dL) at the Screening visit; (NOTE: patients may not have received any growth factors or blood transfusions within 7 days of the hematologic laboratory values obtained at the Screening visit)

5.4 Regulatory Criteria

Patients or their legally authorized representative must be informed of the investigational nature of this study and must sign and give written informed consent in accordance with institutional and federal guidelines. Voluntary written informed consent must be obtained before registration or performance of any study-related procedure not part of normal medical care, with the understanding that the patient may withdraw consent at any time without prejudice to future medical care.

6.0 OVERALL STUDY DESIGN AND PLAN

This study is a phase 2 open label efficacy and safety clinical trial evaluating the combination of oral enzalutamide (160 mg/day) and a 5-ARI either dutasteride (0.5 mg/day) or finasteride (5mg/day)in patients with systemic PCa. The study will enroll patients at two sites: University of Rochester Medical Center and the clinical cancer

center at the Froedtert & Medical College of Wisconsin. Approximately 40 patients will be enrolled.

Patients will receive study treatment until disease progression is documented and confirmed as defined by 1) PSA rise **with or without** radiographic evidence of disease progression or 2) the occurrence of a skeletal-related event. The occurrence of an adverse event, where continued administration of study drug is deemed not in the patient's best interest by the investigator and/or the sponsor, will also result in the removal of the patient from therapy. All patients will be treated with the study drug for a minimum of 12 weeks before assessment for disease progression unless the patient develops significant treatment-related toxicity or worsening symptoms due to rapid disease progression.

The consensus guidelines of the Prostate Cancer Clinical Trials Working Group 2 have been taken into consideration for the determination of disease progression in the study.(62) Disease progression based on PSA is defined as an increase in the PSA that is $\geq 25\%$ **and** $\geq 2\text{ng/ml}$ above the nadir PSA value. A confirmatory PSA is required three or more weeks later and it should demonstrate persistent elevation. Patients should continue on study treatment until this confirmatory PSA testing is performed to document PSA progression. Radiographic disease progression is defined by Response Evaluation Criteria in Solid Tumors (RECIST 1.1) (Appendix B) for soft tissue disease or the appearance of two or more new bone lesions on bone scan.

The following assessments will be performed during the course of the clinical trial as detailed in section 8.0: soft tissue and visceral disease on computed tomography (CT) scan or on magnetic resonance imaging (MRI), bone disease on radionuclide bone scans, skeletal related events, analgesics use, Comprehensive Geriatric Assessment, Functional Assessment of Cancer Therapy-Prostate (FACT-P) and PSA. Radiologic studies will be read on site. Each site will ideally designate the same radiologist who will evaluate the images for any one patient for the duration of the trial. Repeat imaging for assessment of radiographic progression is not required once radiographic progression is determined.

Patients without radiographic evidence of metastatic disease at the time of enrollment will obtain repeat imaging only at the time of documented PSA progression or as clinically indicated. For patients with radiographic evidence of metastatic disease at enrollment, disease assessment with radiographic studies should be performed as detailed in section 8.0 and may be performed more frequently if clinically indicated. Chest imaging may include either chest X-ray or CT chest at the discretion of the treating physician.

CGA will be used to capture baseline health status prior to treatment and repeated at pre-specified intervals to document toxicities related to treatment and to assess any changes in functional status from baseline. A geriatric oncologist or his/her designee at each respective institution will administer CGA.

Forty patients will be recruited and treated until disease progression or meeting any reason for removal from treatment (see section 7.4). The primary efficacy end-point for this trial is PSA progression-free survival (PFS), which is defined as the length of time that a given subject will be alive and free from PSA progression as defined above in section 6.0.

Throughout the study, safety and tolerability of study treatment will be assessed by the monitoring of adverse events, vital signs, physical examinations, and laboratory studies per study calendar. The PI will monitor safety data on an ongoing basis. Patients will have a Safety Follow-up visit 30 days after their last dose of study drug or prior to the initiation of another systemic antineoplastic therapy, whichever occurs first. Serious adverse events will be collected for 30 days after the patient's last dose of study drug. After treatment discontinuation, subsequent antineoplastic therapy and survival status will be assessed.

7.1 Treatment

All patients will receive either a combination of enzalutamide 160 mg oral daily and dutasteride 0.5 mg oral daily or enzalutamide 160 mg oral daily and finasteride 5 mg oral daily until disease progression or other reasons for removal from treatment protocol. (see section 7.4). The type of 5-AR inhibitor used for each patient will depend on insurance approval. Dutasteride will be the 5AR-Inhibitor of choice given its slightly better efficacy. If for any reason dutasteride cannot be obtained, finasteride would be administered.

7.2 Prior and Concomitant Therapy

All concomitant medication(s) including any medications taken within four weeks prior to the Day 1 visit will be collected. Concomitant medications include all vitamins, herbal remedies, over the counter, and prescription medications. Intermittent or as needed (prn) use of any medication during the study indicates the possible occurrence of an adverse event and must be noted as such and be recorded.

7.2.1 Prohibited Medications

The following medications are prohibited within 4 weeks prior to the start of study drug treatment and are prohibited during the course of the study:

- Chemotherapeutic, immunotherapeutic and biologic agents
- Systemic glucocorticoids greater than the equivalent of 10 mg per day of prednisone/prednisolone (unless needed for stress steroids or to treat presumed adrenal insufficiency)
- Estrogens
- Herbal medications that may affect PSA levels (i.e., saw palmetto)
- Androgens (testosterone, dihydroepiandrosterone [DHEA], etc.).

Use of bisphosphates or rank-ligand inhibitor is allowed but doses should be documented during the study period.

The use of strong or moderate CYP2C8 or CYP3A4 inducers or inhibitors (see Appendix F) is prohibited while on study for patients receiving dutasteride.

Patients on therapies known to be weak inhibitors/inducers or narrow-therapeutic-index substrates of CYP2C8 or CYP3A4 should be evaluated for clinically significant drug interactions, but may participate in the study with appropriate monitoring and management.

Deviation from the above guidelines should occur only if absolutely necessary for the well-being of the patient. Any deviations to the medication/treatment guidelines are to be recorded.

7.2.2 Permitted Medications

Patients are allowed to take prescription medications as long as they are not considered to interact with the study drug as listed in the prohibited medication list. All prescription medications should be reported to the study personnel. Patients concomitantly using warfarin will need to have their INR monitored closely.

7.2.3 Non Drug Therapies

Patients are allowed to take over the counter supplements, including multivitamins. All non-prescription therapies should be reported to the study personnel

7.3 Treatment Compliance

Study drug accountability will be performed at pre-specified study visits to document compliance with the dosing regimen. Patients will be asked to bring back all remaining study drug and all study drug packaging at the beginning visit of each cycle for drug

accountability. Treatment compliance will be defined as the number of capsules taken during the study divided by the expected number of capsules, multiplied by 100%. Capsules that are not returned will be considered to have been taken, unless otherwise specified. Compliance will be assessed at each specified visit by review of a pill diary and/or by questioning patients as to compliance. Compliance will be recorded in the source documentation.

7.4 Criteria for Removal from Protocol Treatment

- Disease progression as defined by 1) PSA rise **with or without** radiographic evidence of disease progression or 2) the occurrence of a skeletal-related event (see section 6.0)
- Unacceptable toxicity very likely related to studydrugs
- Off study treatment for ≥ 30 days
- Initiation of new systemic treatment for PCa
- The patient may withdraw from the study at any time for any reason
- Death
- Product not available
- Lost to follow-up
- Decision by sponsor

7.5 Treatment Discontinuation

Patients will be advised in the written informed consent form that they have the right to withdraw from study drug treatment at any time without prejudice, or may be withdrawn at any time at the discretion of the investigator or the sponsor. If medically indicated, the investigator or the sponsor may withdraw study drug from a patient in the event of an intercurrent illness, adverse event, other reasons concerning the health or well-being of the patient, or in the case of lack of cooperation, non-compliance, protocol violation, or other administrative reasons.

Patients removed from therapy for any reason should continue to be followed for the collection of safety data as outlined in the adverse event reporting section and the Safety follow-up visit procedures. For patients who decline further clinic study visits, telephone contact should be attempted to review for adverse events 30 days after the last dose of study drug or prior to the initiation of another systemic antineoplastic therapy, whichever occurs first. All serious adverse events will be followed until resolution, until the event has stabilized and/or become chronic, until it has been determined that the event was caused by an etiology other than the study drug, or through 30 days, whichever comes first.

Reasonable effort should be made to contact any patient lost to follow-up during the course of the study in order to complete study-related assessments and retrieve any

outstanding data and study drug. Following unsuccessful telephone contact, an effort to contact the patient by mail using a method that provides proof of receipt should be attempted. Such efforts should be documented in the source documents. All reasons for discontinuation of treatment must be documented.

7.6 Follow up Period

All patients will be followed until study closure, death, or patient's decision to withdraw consent. Data will be collected at pre-specified intervals as detailed in the study calendar (see section 8.0) to assess safety and efficacy. After treatment discontinuation, subsequent antineoplastic therapy and survival status will be assessed for the duration of follow up.

7.7 Unscheduled Visits

Unscheduled visits may be performed at any time during the study whenever necessary to assess for or follow-up on adverse events, at the patient's request, or as deemed necessary by the investigator. The date and reason for the unscheduled visit should be recorded in the source documentation. The following activities can be completed at unscheduled visits (other than those exclusively for return or re-supply of study drug):

- 12-lead ECG (if medically indicated);
- Vital signs (blood pressure, heart rate, respiratory rate, temperature);
- Laboratory assessment (hematology and chemistry);
- Enquire from the patient and record the time that study medication was taken on the preceding 2 days;
- Brief history and physical examination; ECOG performance status;
- Record concomitant medications; Record adverse event

8.0 STUDY CALENDAR@

Study Day ^a	PRE STUD Y ^a	Cycle 1 Cycle 2 Cycle 3 Cycle 4 Cycle 5 Cycle 6 Cycle 7 Cycle 8 Cycle 9										β			
		W	W	W	W	W	W	W	W	W	W	W	FU Prior to Progression ^a	Safety FU Within 30 days after last treatment dose	FU After Progression ^a
REQUIRED STUDIES															
PHYSICAL															
History and Physical Exam	X	X	X	X	X	X	X	X	X	X	X	X	X	X	X
Weight and Performance Status	X	X	X	X	X	X	X	X	X	X	X	X	x	X	
Blood Pressure	X	X	X	X	X	X	X	X	X	X	X	X	x	X	
Disease Assessment	X				X	X	X	X	X	X	X	X	X	X	
Toxicity Notation		X	X	X	X	X	X	X	X	X	X	X	x	X	
Comprehensive Geriatric Assessment ^w	X			X			X							x	
LABORATORY															
Serum PSA	X		X	X	X	X	X	X	X	X	X	X	X	X	
Serum Testosterone	X		X	X			X							X	
Serum Dihydrotestosterone	X						X							X	
CBC/Differential /Platelets/Hemoglobin	X		X	X	X		X	X	X	X	X	X	x	X	
Comprehensive Metabolic Panel	X		X	X	X		X	X	X	X	X	X	x	X	
X-RAY and SCANS															
DEXA ^a	X											X			
CT of Abdomen and Pelvis [#]	X				X			X					x [#]		
Bone scan [#]	X				X			X					x [#]		
Chest Imaging [#]	X				X			X					x [#]		
TREATMENT															
Enzalutamide ^e		X		X	X	X	X	X	X	X	X	X			
5-AR inhibitor ^e		X		X	X	X	X	X	X	X	X	X			
Prophylactic Breast Radiation [¶]	X														

@ Study visits from the Covid-19 pandemic (starting in March 2020) and moving forward can be performed via telemedicine technology. Study team should adhere to study procedures as outlined by study calendar above except for weight and physical examination, including vital signs (e.g. temperature, heart rate, pulse oximetry, and respiratory rate). We expect subjects to report blood pressure measurements performed by themselves or care providers within +- 7 days of study visit while on study treatment. Study drug may be shipped to patients undergoing a telemedicine visit.

¤ Except for week 1 visit, there is a window of +/- 4 weeks for subsequent follow up visits. Prestudy labs/visit to be no more than 3 weeks prior to cycle 1, Day 1 Pre enrollment scans must be obtained within 28 days of day1 treatment/

¤ Patients off protocol treatment secondary to reasons other than progression will have physical exams and PSA for disease assessment performed every 6 months for first year and as clinically indicated thereafter.

¤ Patients with stable disease and on protocol treatment beyond week 97 will be followed every 12 weeks until disease progression.

¤ After disease progression, follow-up will occur every 6 months (+/- 2 months) for first year after disease progression and as clinically indicated thereafter. Each subsequent antineoplastic therapy and survival status are the only required data point following progression.

¤ Comprehensive geriatric assessment (CGA) will be performed at baseline, end of cycle 1 and every 24 weeks during the study protocol until week 61 and at the time of progression. FACT-P will be performed along with CGA

¤ DEXA scan must be obtained within 2 years prior to registration for all patients. Follow-up DEXA scans should be obtained after 2 years of protocol treatment for patients not receiving denosumab or bisphosphonates. DEXA scan is not indicated for those who are on treatment with bisphosphonates or denosumab.

¤ For patients without radiographic evidence of metastatic disease at enrollment of study protocol, disease assessment with radiographic studies are not necessary unless there is evidence of PSA progression (see Section 6.0) or clinically indicated. For patients with radiographic evidence of metastatic disease at enrollment of study protocol, disease assessment with radiographic studies should be performed as indicated in the above study calendar and may be performed more frequently if clinically indicated by the same methods used at baseline. Chest Imaging may include either chest X-ray or CT chest at the discretion of the treating physician. After week 97, for patients with stable PSA, scans to be performed at the time of progression or as clinically indicated

¤ Treatment will be given daily and will continue until disease progression or other reason for discontinuation of protocol treatment (see Section 7.4) Study drug will be dispensed every 12 +/- 4 weeks and a 120 day supply of medication will be provided at each visit.

¶ This procedure is not mandatory but should be discussed with all patients enrolled in the protocol and can also be considered during the treatment course to prevent further worsening of breast tenderness when considered appropriate..

¤ Followed until death, study closure, or withdrawal of consent.

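### The telemedicine footnote waives heart rate at pre-study and Day 1 visits although eligibility depends on it, and leaves unclear how pre-treatment blood pressure is obtained remotely

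*Combined protocol and SAP*

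**What the plan says.** The footnote marked @ is attached to the title of the Section 8.0 calendar, so it applies to every column. It opens: "Study visits from the Covid-19 pandemic (starting in March 2020) and moving forward can be performed via telemedicine technology". At such visits the team follows the calendar "except for weight and physical examination, including vital signs (e.g. temperature, heart rate, pulse oximetry, and respiratory rate". It then says: "We expect subjects to report blood pressure measurements performed by themselves or care providers within +- 7 days of study visit while on study treatment", and finally: "Study drug may be shipped to patients undergoing a telemedicine visit".

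Exclusion 15 in Section 5.3.3 bars men with a systolic pressure under 86 mmHg "or bradycardia with a heart rate $<$ 50 beats per minute". It also bars uncontrolled hypertension, defined by a resting systolic pressure of 170 mmHg or a diastolic pressure above "105 mmHg at the Screening or Study Day 1 visit". Section 5.1 makes every criterion a condition of registration, and Section 5.3 bars anyone who meets an exclusion. The footnote does not mention either section.

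In the calendar, the history and physical examination, the weight and performance status, and the "Blood Pressure" rows are each marked at pre-study and at the first treatment visit. There is no row for heart rate or for vital signs as a group. Section 6.0 says vital signs are monitored according to the calendar.

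**The concern.** Eligibility asks for a heart rate, and the schedule says that a remote visit need not collect one. The waiver covers the visits at which eligibility is settled, and drug may be shipped after a remote visit with no exception for the first supply. A site could follow the footnote exactly and have no scheduled reading with which to document the bradycardia limit. It would also have no stated way of obtaining the blood pressure values before treatment.

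These limits matter in this population. Section 1.2 gives heart disease among the reasons men were not given ADT, and Section 3.1.4 lists hypertension among the events possibly related to enzalutamide. At stake are the documentation of a safety exclusion and the pre-treatment reference values for later toxicity assessment. No effect on the PSA-PFS analysis is claimed.

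**Working it through.** No calculation underlies the point, so the check sets the passages side by side.

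**1. Scope of the footnote.** It covers study visits in general. The next footnote, on visit windows, does carve out the week 1 visit, so the authors stated an exception where they wanted one. Here there is none for pre-study or Day 1.

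**2. The exclusion 15 limits against the schedule.**

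| Limit | Visit named in exclusion 15 | Calendar source at pre-study | Treatment in the footnote |
|---|---|---|---|
| Heart rate below 50 per minute | None | Physical examination only | Waived by name |
| Systolic below 86 mmHg | None | Own row | Not named as waived; remote method stated for the treatment period only |
| Systolic 170 mmHg | Screening or Day 1 | Own row | As above |
| Diastolic above 105 mmHg | Screening or Day 1 | Own row | As above |

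**3. Heart rate.** The footnote's wording makes vital signs part of the physical examination, and that examination is marked at pre-study. Because there is no separate heart-rate row, it is the only scheduled source of the reading. Waiving it at a remote pre-study visit removes that source, while Section 5.1 still requires the criterion to be met.

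**4. Blood pressure before treatment.** Its separate row and its absence from the list of waived signs favour reading it as still required. Two things blur this. The list gives examples only, and Section 7.7 counts blood pressure among vital signs. Also, the self- or carer-report sentence is limited to men already on treatment, so a remote pre-study reading has no stated method.

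**5. Blood pressure on Day 1.** If the reporting sentence is applied to Day 1, the window runs from 7 days before to 7 days after the visit: 7 + 1 + 7 = 15 calendar dates, of which 7 come after the visit. If the first dose is taken on Day 1, a reading on any of those 7 dates satisfies the window but follows the dose.

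**6. Weight.** It is waived by name, with no exception for baseline. The geriatric assessment is not waived, however, and its nutrition form in Appendix E asks the man's current weight. What can be missing is a weight measured at the visit, not every record of weight.

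**7. Number affected.** Section 6.0 plans about 40 men at two sites. The documents do not say how many were screened or started after March 2020, or how many of those visits were remote. The count could be zero.

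**The case against.** The strongest reply is that nothing is really waived for eligibility. Telemedicine is optional, whereas Sections 5.1 and 5.3 are mandatory, and a footnote on how visits are conducted does not amend them. A site can comply with everything by seeing the man in person, or by obtaining a pulse elsewhere, since the heart-rate limit names no visit. The references to on-treatment readings and drug shipment suggest the authors had treated men in mind. Pre-study blood tests, scans and the SPPB are not waived, so most men will attend somewhere anyway. And the calendar has no heart-rate row even for in-person visits.

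Much of this stands, and it rules out three stronger readings:

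- A reader might infer that a man may properly start drug with every exclusion 15 limit unmeasured. Section 5.1 still forbids registering a man whose criteria are not met, and blood pressure remains scheduled.
- A reader might infer that the footnote and exclusion 15 cannot both be followed. They can, because the footnote is permissive.
- A reader might infer that baseline BMI is lost. The geriatric assessment that contains it is still required and asks for weight.

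The reply does not remove the heart-rate problem. The lack of a separate row makes the physical examination the only scheduled source, and the footnote lifts that examination while naming heart rate. Attendance for blood tests or scans does not oblige anyone to take or record a pulse. If only treated men were meant, the footnote does not say so.

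**Conclusion.** The point holds in a limited form. For heart rate, the schedule waives by name, at a remote pre-study or Day 1 visit, a reading that exclusion 15 and Section 5.1 need. For blood pressure, the defect is ambiguity rather than waiver: the reading is still scheduled, but the remote method is worded only for the treatment period, and on Day 1 its window extends past the visit.

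This is a waiver drawn too broadly, not the removal of the eligibility check. It rests on taking the footnote's placement on the calendar title at face value and on the absence of any exception in its text. The documents do not support saying that the excluded groups cannot be identified. The practical reach is unknown and may be nil. The point still merits a correction because a safety exclusion is involved and the change is small.

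**What to change.** Reconcile the Section 8.0 footnote with exclusion 15 and Section 5.1. Either of two one-sentence changes would do:

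- limit the footnote's waiver to visits after Day 1; or
- state in the footnote that the exclusion 15 readings and baseline weight are not waived at pre-study or Day 1, and must be documented before first drug is dispensed or shipped.

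The exclusion limits stay as they are, and the choice between the two is the sponsor's. If any man was screened or started remotely after March 2020, the sponsor should also record how exclusion 15 was verified for him.

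The cost is one sentence and possibly one in-person or local contact before the first dose. Screening blood tests, scans and the SPPB largely require such a contact already.

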respectively. In addition to the number and percentage of subjects alive and without PSA progression at 1 and 2 years of follow-up, we will report separately numbers and percentages of subjects alive and with PSA progression, dead without PSA progression, and dead with PSA progression. The causes of death and the incidence of clinical progression will also be reported.

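### Section 10.1 promises causes of death and the incidence of clinical progression, but the study calendar requires neither to be recorded once a man has progressed

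*Combined protocol and SAP*

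**What the plan says.** Section 10.1 sets out two kinds of descriptive report beside the primary PSA-PFS estimate. The first is a table at 1 and 2 years that crosses vital status with PSA progression. Besides men alive and free of progression, it counts those "alive and with PSA progression, dead without PSA progression, and dead with PSA progression". The second is a single sentence with no time limit: "The causes of death and the incidence of clinical progression will also be reported".

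The study calendar in section 8.0 governs what is collected after progression. On timing, its footnote says: "After disease progression, follow-up will occur every 6 months (+/- 2 months) for first year after disease progression and as clinically indicated thereafter". On content, it says: "Each subsequent antineoplastic therapy and survival status are the only required data point following progression".

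Two other statements set how long follow-up lasts. Section 7.6 says "All patients will be followed until study closure, death, or patient's decision to withdraw consent", and adds that "subsequent antineoplastic therapy and survival status will be assessed for the duration of follow up". A further calendar footnote reads "Followed until death, study closure, or withdrawal of consent".

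**The concern.** The analysis section commits to two outcomes that the data-collection section leaves off its list of required items. The footnote's word for that list is exclusive, so a site that follows it exactly has no duty to record why a progressed man died, or when his disease became clinically or radiographically evident.

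In men aged 65 and over who were judged poor candidates for ADT, cause of death is what separates deaths from prostate cancer from deaths from other illness. If it is recorded mainly for deaths on or shortly after treatment, the reported distribution of causes describes only those deaths. Likewise, an incidence of clinical progression that mostly stops counting at PSA progression will be too low, and the reader could not tell by how much. A lesser worry is that survival status at 2 years has no set contact date for the men who progress earliest.

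**Working it through.** The plan states no figure on this point that could be reproduced. The main check is to match each promised report to its required source after PSA progression.

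| Promised in section 10.1 | Required source after PSA progression |
|---|---|
| PSA-progression state at 1 and 2 years | Already fixed once progression is confirmed |
| Vital state at 1 and 2 years | Survival status (calendar footnote; section 7.6), to death, closure or withdrawal |
| Cause of death | SAE report only |
| Incidence of clinical progression | None |

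**Cause of death.** Section 11.4 asks for it when a death is reported as an SAE. That section ends SAE collection 30 days after the last dose or at the start of another systemic anticancer treatment, whichever is first; section 6.0 also gives 30 days. Sections 6.0 and 7.4 end treatment on a PSA rise, whether or not imaging shows progression, once a second PSA at least three weeks later confirms it. A death more than 30 days after that stop, or after new therapy begins, therefore has a required status but no required cause.

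**Clinical progression.** Section 10.1 does not define the term; I read it as including radiographic and skeletal events. Those occurring before or at PSA progression have a route to the record. Men with metastases at entry are scanned on the calendar, men without them are scanned at PSA progression (section 6.0), and a skeletal-related event itself ends treatment (section 7.4). After PSA progression no disease-status item is required. A man whose PSA progresses with clear scans, and who develops bone metastases later, need not be counted.

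**How many men have no fixed contact date at 2 years.** Inputs are N = 40 and 1-year PSA-PFS of 72% (alternative) and 50% (null), all from section 10.1, and fixed contacts ending 12 months after progression (±2 months) from the calendar.

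1. Last fixed contact = month of progression + 12. To reach month 24, progression must fall at month 12 or later.
2. Men with a PSA-PFS event before month 12 = 40 × (1 − S(1 year)).
 - Alternative: 40 × (1 − 0.72) = 11.2.
 - Null: 40 × (1 − 0.50) = 20.0.
3. Moving the cut-off to months 10 and 14 for the window, and assuming exponential times, 40 × (1 − S(1)^(t/12)) gives:
 - Alternative: 9.6 at month 10 and 12.7 at month 14.
 - Null: 17.6 at month 10 and 22.2 at month 14.

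Step 2 uses the plan's 1-year rates directly and needs no distributional assumption. It is an upper bound on early progressors because PSA-PFS events include deaths, and a man who has died has a known state.

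**How many men the cause-of-death and clinical-progression gap could touch.** This gap is open to every man who progresses, early or late. PSA-PFS events by 2 years, again counting deaths, are 40 × (1 − 0.40) = 24 using the 2-year value in the plan's own margin-of-error expression. Under exponential times they are 40 × (1 − 0.72²) = 19.3 and 40 × (1 − 0.50²) = 30.

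**The case against.** A reader might infer that the 2-year table cannot be completed for early progressors. The documents do not support that. The table needs only PSA state and vital state. The first is settled at progression. The second is required after progression and, under section 7.6, assessed throughout follow-up. A contact at any later date, including one at study closure, establishes whether a man was alive at month 24. Section 7.5 also requires men lost to follow-up to be traced by telephone and then by mail.

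Nor does the footnote contradict section 7.6. One sets how often men are contacted and the other sets how long they are followed. Read together, contact after the first year is "for first year after disease progression and as clinically indicated thereafter", with status still owed until closure. The timing is left open; follow-up does not stop.

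It can also be said that these are supplementary descriptive counts. No objective in section 2.0 concerns overall survival, cause of death or clinical progression after PSA progression. Some clinical progression is captured, and section 10.1 does not say that the incidence must extend past PSA progression. A required minimum does not forbid collecting more. The case report forms and the Data Management Plan (section 14.9) are not among the documents, and a survival form might already record cause. The calendar grid, as far as the extracted table can be read, also seems to mark a history and physical examination after progression.

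All of this limits the point without removing it. A visit that may reveal progression is not a requirement to record it, and a form that may have a cause-of-death field does not change a footnote that excludes it. The protocol as written promises two reports whose inputs it does not require.

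**Conclusion.** The point holds in a narrow form. After PSA progression, cause of death outside the SAE window and any later clinical, radiographic or skeletal progression have no required source. The two reports promised in section 10.1 would therefore be incomplete for men who progress. How incomplete cannot be computed, because the plan gives no post-progression death or metastasis rate. The men potentially affected by 2 years number up to 24 of 40 on the plan's own 2-year value (19 to 30 from the 1-year rates under exponential times), with deaths included as events.

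The 2-year table of vital status by PSA progression can be completed from required data. Its weakness is one of scheduling: at most about 11 of 40 men at the 72% rate, or 20 of 40 at 50%, have no fixed contact date that reaches month 24, counting deaths as progressions and ignoring the 2-month window. A reader might take these counts as the share of the cohort with missing 2-year status, but they count men without an appointment date, not men with missing data. Primary PSA-PFS is unaffected for men who have progressed, because their event has already been recorded.

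This rests on reading the footnote literally and on the unseen forms adding nothing to it.

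**What to change.** In the after-progression footnote of section 8.0, add two required items: date and cause of death, and date and type of first clinical or radiographic progression known from routine care. State that no extra scans are asked for. Add a telephone or chart survival check that covers month 24 from Day 1, so that the 2-year table rests on a set contact.

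If the sponsor prefers not to collect these items, limit the section 10.1 sentence on causes of death and clinical progression to the period in which they are collected, and say so when reporting them.

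The cost is a few case report form fields and one or two telephone or chart contacts per early progressor. No visits, scans or patients are added.
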